6.7 Intervention After the End of the Study

Not applicable.

6.8 Clinical Supplies Disclosure

This study is open-label; therefore, the participant, the study-site personnel, the Sponsor, and/or designee are not blinded. Study intervention (name, strength, or potency) is included in the label text; random code/disclosure envelopes or lists are not provided.

6.9 Standard Policies

Not applicable.

7 DISCONTINUATION OF STUDY INTERVENTION AND PARTICIPANT WITHDRAWAL

7.1 Discontinuation of Study Intervention

Discontinuation of study intervention does not represent withdrawal from the study.

As certain data on clinical events beyond study intervention discontinuation may be important to the study, they must be collected through the participant's last scheduled follow-up, even if the participant has discontinued study intervention. Therefore, all participants who discontinue study intervention before completion of the protocol-specified treatment period will still continue to be monitored in this study and participate in the study visits and procedures as specified in Section 1.3 and Section 8.12.3 unless the participant has withdrawn from the study Section 7.2.

Participants may discontinue study intervention at any time for any reason or be discontinued from the study intervention at the discretion of the investigator should any untoward effect occur. In addition, a participant may be discontinued from study intervention by the investigator or the Sponsor if study intervention is inappropriate, the study plan is violated, or for administrative and/or other safety reasons.

Participants must complete the Treatment Crossover Period (see Section 4.1) including all 3 MK-3475A SC and 3 pembrolizumab IV cycles in order to complete the C6D1 PPQ. Any participant who does not complete the Treatment Crossover Period will be discontinued from study intervention.

A participant must be discontinued from study intervention, but continue to be monitored in the study for any of the following reasons:

- The participant requests to discontinue study intervention.
- Any prohibited concomitant therapy outlined in Section 6.5.
- Any prolonged interruption of study intervention beyond the permitted periods, for irAE management or other allowed dose interruptions, as noted in Section 6.6.1, require Sponsor consultation before restarting treatment. If treatment will not be restarted, the participant will continue to be monitored in the study and the reason for discontinuation of study intervention will be recorded in the medical record.
- The participant has a medical condition or personal circumstance which, in the opinion of the investigator and/or Sponsor, placed the participant at unnecessary risk from continued administration of study intervention.
- The participant has a confirmed positive serum pregnancy test.
- Any progression or recurrence of malignancy, or any occurrence of another malignancy that requires active treatment.

- Any study intervention-related toxicity specified as a reason for permanent discontinuation as defined in the guidelines for dose modification due to AEs in Section 6.6.

Discontinuation from study intervention is “permanent.” Once a participant is discontinued from study intervention, they shall not be allowed to restart study intervention.

7.2 Participant Withdrawal From the Study

A participant must be withdrawn from the study if the participant withdraws consent from the study.

If a participant withdraws from the study, they will no longer receive study intervention or be followed at scheduled protocol visits.

Specific details regarding procedures to be performed at the time of withdrawal from the study, are outlined in Section 8.1.9. The procedures to be performed should a participant repeatedly fail to return for scheduled visits and/or if the study site is unable to contact the participant are outlined in Section 7.3.

7.3 Lost to Follow-up

If a participant fails to return to the clinic for a required study visit and/or if the site is unable to contact the participant, the following procedures are to be performed:

- The site must attempt to contact the participant and reschedule the missed visit. If the participant is contacted, the participant should be counseled on the importance of maintaining the protocol-specified visit schedule.
- The investigator or designee must make every effort to regain contact with the participant at each missed visit (eg, telephone calls and/or a certified letter to the participant’s last known mailing address or locally equivalent methods). These contact attempts should be documented in the participant’s medical record.

8 STUDY ASSESSMENTS AND PROCEDURES

- Study procedures and their timing are summarized in the SoA.
- Adherence to the study design requirements, including those specified in the SoA, is essential and required for study conduct.
- The investigator is responsible for ensuring that procedures are conducted by appropriately qualified (by education, training, and experience) staff. Delegation of study-site personnel responsibilities will be documented in the Investigator Trial File Binder (or equivalent).
- All study-related medical decisions must be made by an investigator who is a qualified physician.
- All screening evaluations must be completed and reviewed to confirm that potential participants meet all eligibility criteria. The investigator will maintain a screening log to record details of all participants screened and to confirm eligibility or record reasons for screening failure, as applicable.
- Procedures conducted as part of the participant's routine clinical management (eg, blood count) and obtained before providing documented informed consent may be used for screening or baseline purposes provided the procedures meet the protocol-specified criteria and were performed within the time frame defined in the SoA.
- Additional evaluations/testing may be deemed necessary by the investigator and or the Sponsor for reasons related to participant safety. In some cases, such evaluation/testing may be potentially sensitive in nature (eg, HIV, hepatitis C), and thus local regulations may require that additional informed consent be obtained from the participant. In these cases, such evaluations/testing will be performed in accordance with those regulations.
- The maximum amount of blood collected from each participant over the duration of the study will not exceed the volume mentioned in the laboratory manual.
- Repeat or unscheduled samples may be taken for safety reasons or for technical issues with the samples.

8.1 Administrative and General Procedures

8.1.1 Informed Consent

The investigator or medically qualified designee (consistent with local requirements) must obtain documented informed consent from each potential participant prior to participating in this clinical study or FBR. If there are changes to the participant's status during the study (eg, health or age of majority requirements), the investigator or medically qualified designee must ensure the appropriate documented informed consent is in place.

8.1.1.1 General Informed Consent

Informed consent given by the participant must be documented on a consent form. The form must include the study protocol number, study protocol title, dated signature, and agreement of the participant and of the person conducting the consent discussion.

A copy of the signed and dated informed consent form should be given to the participant before participation in the study.

The initial ICF, any subsequent revised ICF, and any written information provided to the participant must receive the IRB/IEC's approval/favorable opinion in advance of use. The participant should be informed in a timely manner if new information becomes available that may be relevant to the participant's willingness to continue participation in the study. The communication of this information will be provided and documented via a revised consent form or addendum to the original consent form that captures the participant's dated signature.

Specifics about the study and the study population are to be included in the study informed consent form.

Informed consent will adhere to IRB/IEC requirements, applicable laws and regulations, and Sponsor requirements.

8.1.2 Inclusion/Exclusion Criteria

All inclusion and exclusion criteria will be reviewed by the investigator, who is a qualified physician, to ensure that the participant qualifies for the study.

8.1.3 Participant Identification Card

All participants will be given a participant identification card identifying them as participants in a research study. The card will contain study-site contact information (including direct telephone numbers) to be used in the event of an emergency. The investigator or qualified designee will provide the participant with a participant identification card immediately after the participant provides documented informed consent. At the time of intervention randomization, site personnel will add the treatment/randomization number to the participant identification card.

The participant ID card also contains contact information for the emergency unblinding call center so that a health care provider can obtain information about study intervention in emergency situations where the investigator is not available.

8.1.4 Medical History

A medical history will be obtained by the investigator or qualified designee. The medical history will collect all active conditions and any condition diagnosed within the prior 10 years that the investigator considers to be clinically important. Details regarding the disease for which the participant has enrolled in this study will be recorded separately and not listed as medical history.

If a medical condition is diagnosed at the time of screening due to the physical examination, laboratory tests, radiologic assessment, other assessment, and/or a combination of these evaluations, the medical condition is to be recorded as a baseline condition along with the participant's other medical history unless due to any protocol-specified intervention (eg, procedure, washout, or run-in treatment including placebo run-in).

8.1.4.1 Tobacco Use Assessment

Definitions for cigarette use are as follows [Land, S. R., et al 2016]:

- Current smokers: persons who report smoking ≥ 100 cigarettes during their lifetime and who, at the time of screening, reported smoking every day or some days within the last year.
- Former smokers: persons who report smoking ≥ 100 cigarettes during their lifetime and who, at the time of screening, had stopped smoking 1 year prior.
- Never smokers: persons who report smoking < 100 cigarettes during their lifetime.

8.1.5 Prior and Concomitant Medications Review

8.1.5.1 Prior Medications

The investigator or qualified designee will review prior medication use, including any protocol-specified washout requirement, and record prior medication taken by the participant within 28 days before starting the study. Treatment for the disease for which the participant has enrolled in this study will be recorded separately and not listed as a prior medication.

8.1.5.2 Concomitant Medications

The investigator or qualified designee will record medication, if any, taken by the participant during the study through the Safety Follow-up Visit. In case of SAE, record medication through the 90-day Follow-up Period.

8.1.6 Assignment of Screening Number

All consented participants will be given a unique screening number that will be used to identify the participant for all procedures that occur before randomization. Each participant will be assigned only 1 screening number. Screening numbers must not be reused for different participants.

8.1.7 Assignment of Randomization Number

All eligible participants will be randomly allocated and will receive a randomization number. The randomization number identifies the participant for all procedures occurring after randomization. Once a randomization number is assigned to a participant, it can never be reassigned to another participant.

A single participant cannot be assigned more than 1 randomization number.

8.1.8 Study Intervention Administration

Study intervention(s) will be administered by the investigator and/or an appropriately qualified designee according to the specifications within the pharmacy manual.

8.1.8.1 Timing of Dose Administration

Study interventions should be administered after all procedures and assessments have been completed.

8.1.9 Discontinuation and Withdrawal

Participants who discontinue study intervention before completion of the treatment period should be encouraged to continue to be followed for all remaining study visits as outlined in the SoA and Section 8.12.3.

Participants who withdraw from the study should be encouraged to complete all applicable activities scheduled for the final study visit at the time of withdrawal. Any AEs that are present at the time of withdrawal should be followed in accordance with the safety requirements outlined in Section 8.5.

8.1.10 Participant Blinding/Unblinding

This is an open-label study; there is no blinding for this study. The emergency unblinding call center will be available so that a health care provider can obtain information about study intervention in emergency situations where the investigator is not available.

8.1.11 Calibration of Equipment

The investigator or qualified designee has the responsibility to ensure that any device or instrument used for a clinical evaluation/test during a clinical study that provides information about inclusion/exclusion criteria and/or safety or efficacy parameters shall be suitably calibrated and/or maintained to ensure that the data obtained are reliable and/or reproducible. Documentation of equipment calibration must be retained as source documentation at the study site.

8.1.12 Tumor Tissue for Biomarker Status

The local laboratory will use the tissue sample to ascertain PD-L1 status using the Dako PD-L1 IHC 22C3 pharmDx diagnostic kit. The Dako PD-L1 IHC 22C3 pharmDx assay kit is currently approved to assess PD-L1 status in participants with NSCLC for treatment with pembrolizumab. EGFR, ALK, and ROS1 at the local laboratory must use tumor tissue for testing to confirm absence of sensitizing alterations.

8.2 Questionnaires

Planned time points for all questionnaires are provided in the SoA.

The PPQ and TASQ in this study will be completed by the participant on an eCOA tablet. The implementation of the electronic version will follow all necessary global confidentiality regulations, including the EMA Guideline on computerized systems and electronic data in clinical trials. Refer to the Site Manual for eCOA site level operations.

As the PPQ is the primary and secondary endpoint of this study, completion of the questionnaire must be checked BEFORE the participant leaves the site at the Cycle 6 Visit.

The participant's choice of MK-3475A SC or pembrolizumab IV for the Treatment Continuation Period will be documented on the Participant Choice Questionnaire, administered at the Cycle 6 Visit after study intervention administration and completion of the PPQ and TASQ.

8.3 Imaging Assessments

8.3.1 Tumor Imaging and Assessment of Disease

Throughout this section, the term 'scan' refers to any medical imaging data used to assess tumor burden and may include cross-sectional imaging (such as CT or MRI), medical photography, or other methods as specified in this protocol.

Imaging should be performed per SoC for each tumor type. Treatment beyond disease progression is not allowed.

8.4 Safety Assessments

Details regarding specific safety procedures/assessments to be performed in this study are provided. The total amount of blood/tissue to be drawn/collected over the course of the study (from prestudy to poststudy visits), including approximate blood/tissue volumes drawn/collected by visit and by sample type per participant, can be found in the Laboratory Manual.

Planned time points for all safety assessments are provided in the SoA.

8.4.1 Physical Examinations

A complete physical examination will be conducted by an investigator or medically qualified designee (consistent with local requirements) per institutional standard. Height and weight will also be measured and recorded.

A brief directed physical examination will be conducted by an investigator or medically qualified designee (consistent with local requirements) per institutional standard.

Investigators should pay special attention to clinical signs related to previous serious illnesses.

8.4.1.1 Full Physical Examination

The investigator or qualified designee will perform a complete physical examination during the Screening period. Clinically significant abnormal findings should be recorded as medical history. The time points for full physical exams are described in Section 1.3. After the first dose of study intervention, new clinically significant abnormal findings should be recorded as AEs.

Investigators should pay special attention to clinical signs related to previous serious illnesses.

8.4.1.2 Directed Physical Examination

For cycles that do not require a full physical examination as defined in Section 1.3, the investigator or qualified designee will perform a directed physical examination as clinically indicated prior to study intervention administration. New clinically significant abnormal findings should be recorded as AEs.

Investigators should pay special attention to clinical signs related to previous serious illnesses.

For melanoma participants: The investigator or qualified designee should conduct a visual inspection of local recurrence and palpation of regional lymph nodes to assess regional recurrence.

8.4.1.3 Injection Site Reactions

Any injection-site AE should be reported using standard AE/SAE reporting methods. Injection-site reaction and pain may include, but are not limited to, the following:

- Injection-site redness/erythema
- Injection-site swelling/edema
- Injection-site tenderness/pain/discomfort/irritation
- Injection-site bruising
- Injection-site infection
- Injection-site hard lump (mass, nodule)/induration
- Injection-site inflammation
- Injection-site rash
- Injection-site hematoma/hemorrhage
- Injection-site extravasation
- Injection-site dermatitis
- Injection-site discoloration/pallor

- Injection-site vesicles/ulcers

Any injection-site AEs should be recorded in the AE eCRF.

8.4.2 Vital Signs

The investigator or qualified designee will measure vital signs and weight at Screening, before administration of each dose of study intervention, end-of-treatment, and during the 30-day Safety Follow-up as specified in the SoA.

- VS include temperature, HR, RR, and BP.
- BP and pulse measurements will be assessed with a completely automated device. Manual techniques will be used only if an automated device is not available.
- BP and pulse measurements should be preceded by at least 5 minutes of rest for the participant in a quiet setting without distractions.
- VS will be measured in a semisupine position after 5 minutes rest.

8.4.3 Electrocardiograms

A standard 12-lead ECG will be performed using local standard procedures. The timing of ECG is specified in Section 1.3. Clinically significant abnormal findings should be recorded as medical history. Additional ECGs may be performed as clinically necessary.

8.4.4 Clinical Safety Laboratory Assessments

Refer to Appendix 2 for the list of clinical laboratory tests to be performed and to the SoA for the timing and frequency.

- The investigator or medically qualified designee (consistent with local requirements) must review the laboratory report, document this review, and record any clinically relevant changes occurring during the study in the AE section of the CRF. The laboratory reports must be filed with the source documents. Clinically significant abnormal laboratory findings are those which are not associated with the underlying disease, unless judged by the investigator to be more severe than expected for the participant's condition.
- All protocol-required laboratory assessments, as defined in Appendix 2, must be conducted in accordance with the laboratory manual and the SoA.
- If laboratory values from nonprotocol-specified laboratory assessments performed at the institution's local laboratory require a change in study participant management or are considered clinically significant by the investigator (eg, SAE or AE or dose modification), then the results must be recorded in the appropriate CRF (eg, SLAB).

- For any laboratory tests with values considered clinically significantly abnormal during participation in the study or within 30 days after the last dose of study intervention, every attempt should be made to perform repeat assessments until the values return to normal or baseline or if a new baseline is established as determined by the investigator.

8.4.4.1 Laboratory Safety Evaluations (Hematology, Chemistry and Urinalysis)

Laboratory tests for hematology, chemistry, and urinalysis are specified in Appendix 2.

8.4.5 Pregnancy Testing

- Pregnancy testing:
 - Pregnancy testing requirements for study inclusion are described in Section 5.1.
 - Pregnancy testing (urine and/or serum) should be conducted as per SoA at every protocol treatment cycle during intervention.
 - Pregnancy testing (urine and/or serum) should be conducted at the end of relevant systemic exposure. The length of time required to continue pregnancy testing for each study intervention is:
 - MK-3475A: 120 days
 - Pembrolizumab: 120 days
 - Additional serum or urine pregnancy tests may be performed, as determined necessary by the investigator or required by local regulation, to establish the absence of pregnancy at any time during the participant's participation in the study.

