Arm A	Pembrolizumab	25 mg/mL	200 mg	IV Infusion	Day 1 of each cycle (Q3W) for C4-C6. On completion of C6, participant will receive preferred IMP for up to 17 cycles (melanoma and RCC) or 35 cycles (NSCLC).	Comparator
Arm B	Pembrolizumab	25 mg/mL	200 mg	IV Infusion	Day 1 of each cycle (Q3W) for C1-C3. On completion of C3, participant will be switched to SC.	Comparator
Arm B	MK-3475A	165 mg/mL	395 mg	SC	Day 1 of each cycle (Q3W) for C4-C6. On completion of C6, participant will receive preferred IMP for up to 17 cycles (melanoma and RCC) or 35 cycles (NSCLC).	Test Product

C=cycle; IMP= investigational medicinal product; IV=intravenous; NSCLC= non-small cell lung cancer; Q3W=every 3 weeks; RCC=renal cell carcinoma; SC=subcutaneous.

Other current or former name(s) or alias(es) for study intervention(s) are as follows:
pembrolizumab (KEYTRUDA®, MK-3475, or SCH 900475).

Total Number of Intervention Groups/Arms	2
Duration of Participation	
Each participant will participate in the study for approximately 1 year for adjuvant RCC and melanoma and 2 years for metastatic NSCLC from the time the participant provides documented informed consent through the final protocol-specified contact. After a screening phase of up to 28 days, each participant will be receiving assigned intervention for approximately 1 year for adjuvant RCC and melanoma and 2 years for metastatic NSCLC. After the end of treatment each participant will be followed for up to 90 days.
 
After a screening phase of up to 28 days, each participant will be assigned to receive study intervention until one of the conditions for discontinuation of study intervention is met.
 
After the end of treatment, each participant will be followed for the occurrence of AEs and spontaneously reported pregnancy.

Study Governance Committees:

Executive Oversight Committee	Yes
External Data Monitoring Committee	No
Clinical Adjudication Committee	No

[figure not shown]
Study governance considerations are outlined in Appendix 1.

Study Accepts Healthy Participants: No

A list of abbreviations is in Appendix 11.

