Brain Scan	X	←-----→										
Bone Scan	X	←-----→										
Safety Assessments												
Full Physical Examination Including Weight and Height	X								X			Collect height at Screening only.
Directed Physical Examination		X	X	X	X	X	X	X		X		For melanoma participants: The investigator or qualified designee should conduct a visual inspection of local recurrence and palpation of regional lymph nodes to assess regional recurrence.
Vital Signs	X	X	X	X	X	X	X	X	X	X		Temperature, HR, RR, BP, and weight.
Pregnancy Testing	X	X	X	X	X	X	X	X	X	X		POCBP require a negative pregnancy test before the start of study intervention (within 24 hours for urine or within 72 hours for serum).

Study Period:	Screening Phase	Intervention Phase (21-Day Cycles)							EOT/Discontinuation	Follow-up		Notes
Cycle	Screening (Visit 1)	1	2	3	4	5	6	7 to 35*	At treatment discontinuation	30 days post last dose	90 days post last dose contact	*Cycles 18-35 for NSCLC participants only.
Cycle Day	-28 to -1	1	1	1	1	1	1	1				
Schedule Window		+3	±3	±3	±3	±3	±3	±3				
12-lead ECG	X											Perform at Screening and as clinically indicated thereafter.
ECOG Performance Status	X	X	X	X	X	X	X	X	X	X		Evaluate within 3 days before the planned start of study intervention.
Hematology and Chemistry	X	X	X	X	X	X	X	X	X	X		Collect screening samples within 10 days before the start of study intervention. Collect on-treatment samples and review results within 72 hours before Day 1 of each cycle.
Urinalysis	X											Collect screening samples within 10 days before the start of study intervention.
HBV, HCV, HIV Testing	X											Only perform if required by the local health authority or if known history of infection.
Thyroid Function Tests (TSH, T3, T4)	X		X		X		X	X		X		Screening samples to be collected within 10 days before the first dose of study intervention. Perform at Day 1 of every other cycle starting from C2 until C35 (collect sample within 72 hours prior). Participants may be dosed in subsequent cycles after C1 while thyroid function tests are pending. Free T3 and T4 are acceptable.
PT or INR and aPTT/PTT (baseline only)	X											Collect screening samples within 10 days before the start of study intervention.

Study Period:	Screening Phase	Intervention Phase (21-Day Cycles)							EOT/Discontinuation	Follow-up		Notes
Cycle	Screening (Visit 1)	1	2	3	4	5	6	7 to 35*	At treatment discontinuation	30 days post last dose	90 days post last dose contact	*Cycles 18-35 for NSCLC participants only.

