4. A participant assigned female sex at birth is eligible to participate if not pregnant or breastfeeding, and at least one of the following conditions applies:
- Is not a POCBP
OR
 - Is a POCBP and:
 - Uses a contraceptive method that is highly effective (with a failure rate of $<1\%$ per year), or is abstinent from penile-vaginal intercourse as their preferred and usual lifestyle (abstinent on a long-term and persistent basis), as described in Appendix 5 during the intervention period and for at least 120 days after the last dose of study intervention. The investigator should evaluate the potential for contraceptive method failure (ie, noncompliance, recently initiated) in relationship to the first dose of study intervention. Contraceptive use by POCBPs should be consistent with local regulations regarding the methods of contraception for those participating in clinical studies. If the contraception requirements in the local label for any of the study interventions are more stringent than the requirements above, the local label requirements are to be followed.
 - Has a negative highly sensitive pregnancy test (urine or serum) as required by local regulations within 24 hours (for a urine test) or 72 hours (for a serum test) before the first dose of study intervention. If a urine test cannot be confirmed as negative (eg, an ambiguous result), a serum pregnancy test is required. In such cases, the participant must be excluded from participation if the serum pregnancy result is positive. Additional requirements for pregnancy testing during and after study intervention are in Section 8.4.5.
 - Abstains from breastfeeding during the study intervention period and for at least 120 days after study intervention.
 - Medical history, menstrual history, and recent sexual activity has been reviewed by the investigator to decrease the risk for inclusion of a POCBP with an early undetected pregnancy.

Informed Consent

5. The participant has provided documented informed consent for the study.

Additional Categories

6. The participant can complete the questionnaires without assistance, in the opinion of the primary investigator.
7. Participants who have AEs due to previous anticancer therapies must have recovered to \leq Grade 1 or baseline. Participants with endocrine-related AEs who are adequately treated with hormone replacement or participants who have $<$ Grade 2 neuropathy are eligible.

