- All pregnancies and exposure during breastfeeding, from the time of intervention randomization through the time required to eliminate systemic exposure after cessation of study intervention as described in Sections 5.1 and 8.5.5, or 30 days after cessation of study intervention if the participant initiates new anticancer therapy must be reported by the investigator.
- Additionally, any SAE brought to the attention of an investigator at any time outside the time specified above must be reported immediately to the Sponsor if the event is considered related to study intervention.

Investigators are not obligated to actively seek AEs or SAEs or other reportable safety events in former study participants. However, if the investigator learns of any SAE, including a death, at any time after a participant has been discharged from the study, and the investigator considers the event to be reasonably related to the study intervention or study participation, the investigator must promptly notify the Sponsor.

All initial and follow-up AEs, SAEs, and other reportable safety events will be recorded and reported to the Sponsor or designee within the time frames as indicated in [Table 6](#).

Exception: A positive pregnancy test at the time of initial screening is not a reportable event unless the participant has received study intervention.

Table 6 Reporting Periods and Time Frames for Adverse Events and Other Reportable Safety Events

Type of Event	Reporting Period: Consent to Randomization/ Allocation	Reporting Period: Randomization/ Allocation Through Protocol-specified Follow-up Period	Reporting Period: After the Protocol-specified Follow-up Period	Time Frame to Report Event and Follow-up Information to Sponsor
NSAE	Report if: – due to protocol-specified intervention – causes exclusion – participant is receiving placebo run-in or other run-in treatment	Report all	Not required	Per data entry guidelines
SAE	Report if: – due to protocol-specified intervention – causes exclusion – participant is receiving placebo run-in or other run-in treatment	Report all	Report if: – drug/vaccine related. (Follow ongoing to outcome)	Within 24 hours of learning of event

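### Section 8.4.5 gives 120 days for pregnancy testing, but the Schedule of Activities has its last test at day 30 and no later visit at which to test

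*Protocol*

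**What the plan says.** **Section 8.4.5.** On-treatment testing follows the Schedule of Activities at every cycle. A separate bullet covers the time after treatment: "Pregnancy testing (urine and/or serum) should be conducted at the end of relevant systemic exposure". The text then continues "The length of time required to continue pregnancy testing for each study intervention is" and lists "MK-3475A: 120 days" and "Pembrolizumab: 120 days". A last bullet permits additional tests where the investigator judges them necessary or local regulation requires them, while the person is participating in the study.

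**Section 5.1, criterion 4.** Contraception or abstinence is required "during the intervention period and for at least 120 days after the last dose of study intervention". The same criterion refers sites to Section 8.4.5 for the testing rules during and after treatment.

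**Section 1.3, Table 1.** The pregnancy-testing row is marked at screening, at every treatment cycle, at treatment discontinuation and at 30 days after the last dose. The 90-day column is blank. The note to the row deals only with the test before treatment: "POCBP require a negative pregnancy test before the start of study intervention".

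**Follow-up.** The Synopsis states: "After the end of treatment each participant will be followed for up to 90 days". Section 8.12.3 describes one post-treatment visit, at about 30 days. Section 4.1 describes a telephone call at 90 days for participants who have had serious adverse events.

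**Reporting.** Section 8.5.1 requires pregnancies to be reported "through the time required to eliminate systemic exposure after cessation of study intervention as described in Sections 5.1 and 8.5.5", with a limit of 30 days after cessation if new anticancer therapy starts. Sections 4.1 and 8.5.5 rely on spontaneous reporting of pregnancies.

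**The concern.** A site that follows Table 1 exactly stops pregnancy testing at day 30. A site that follows Section 8.4.5 has a later test to do, but no visit, column or contact at which to do it. Section 8 says that keeping to the schedule is essential and required, and Section 1.3 says that the detail of each scheduled procedure is in Section 8. Neither says which text prevails when they differ.

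What is at stake is a stated safety requirement for participants of childbearing potential. Under the schedule as written, a pregnancy arising after day 30 but within the 120 days would come to light through spontaneous reporting or an optional extra test, not through the test that Section 8.4.5 calls for.

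**Working it through.** No power or sample-size figure is involved. The check compares time points.

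**Step 1: is the day-30 mark read correctly?** Table 1 has 11 time columns: screening, cycles 1 to 6 (six columns), cycles 7 to 35, treatment discontinuation, day 30 and day 90. The pregnancy row has 10 marks. Two other rows confirm the alignment:
- Vital signs also has 10 marks, and Section 8.4.2 says that these measurements end at the 30-day safety follow-up.
- The adverse event review has 11 marks and so reaches day 90.

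The tenth pregnancy mark is therefore day 30 and the day-90 cell is empty. This is not an effect of how the table was extracted.

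**Step 2: does the schedule govern post-treatment testing in Section 8.4.5?** No. The reference to the schedule sits in the bullet on treatment cycles. The post-treatment bullet stands apart and carries its own duration, and Section 5.1 sends sites to it. It cannot be set aside as general text that the schedule overrides.

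**Step 3: where do the 120 days start?** Section 8.4.5 does not say. Section 5.1 counts its own 120 days from the last dose, and the wording of 8.4.5 about the end of exposure fits that. The last dose is used below as an inference.

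**Step 4: the gaps.**

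| From | Day | To the 120-day point |
|---|---|---|
| Last scheduled pregnancy test (Table 1) | 30 | 120 - 30 = 90 days |
| End of stated follow-up (Synopsis) | 90 | 120 - 90 = 30 days |

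The second row treats the Synopsis limit as running from the last dose, as the Table 1 columns do.

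**Step 5: is there a later occasion for the test?** The day-30 visit is the only post-treatment visit described. The adverse event row of Table 1 is marked at day 90, but Section 4.1 describes that contact as a call for participants with serious adverse events, and Table 1 collects vital status at day 90 in case of such an event. On the Section 4.1 wording, a participant without one has no described contact after about day 30.

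**Step 6: reporting.** Section 8.5.1 points to Section 5.1, where 120 days is given, so its window already agrees with Section 8.4.5. Table 6 asks for all pregnancies up to the end of the protocol-specified follow-up period, and after that only for follow-up of those already reported. If that period ends at day 90, as the Synopsis suggests, a pregnancy first found on days 91 to 120 is reportable under 8.5.1 but not provided for in Table 6. Table 6 does not state the length of the period, so this needs checking and is not established as an error.

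**The case against.** The strongest case on the other side has five parts.

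- **Spontaneous reporting is the stated approach.** Sections 4.1 and 8.5.5 say so openly, and reporting does not depend on a scheduled contact. This stands for reporting. It does not supply the test in Section 8.4.5.
- **Extra tests are allowed.** They are optional and limited to the time of participation, so they do not close the gap.
- **Section 8.4.5 may mean one test at the end of exposure.** It sets no frequency. This stands. The 90 days are calendar time between two stated points, not a count of tests lost, and expressing them as a share of the 120 days would suggest continuous testing that the text does not specify. One test at day 120 would still have no visit.
- **The 120-day contraception period needs no visit.** Correct. Section 5.1 does not conflict with the schedule; it serves here only to infer the anchor.
- **The consequence is small.** Exposure in pregnancy is neither an objective nor an endpoint, and the documents do not say how many participants are of childbearing potential. This stands, and the number of people affected cannot be estimated.

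A reader might also infer that safety monitoring as a whole cannot be carried out as scheduled. The documents do not support that: the 30-day window for adverse events and the 90-day window for serious adverse events agree between Table 1 and Section 8.5.1. Nor do they show that countries will work to different end points. The French appendix names a test 30 days after the last dose, in line with Table 1, the Argentine appendix asks for tests at each cycle and at the end of study intervention, and no country appendix sets 120 days.

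**Conclusion.** The protocol contradicts itself on post-treatment pregnancy testing in participants of childbearing potential. Section 8.4.5 gives 120 days; the schedule ends testing at day 30, and no visit is planned at which the later test could be done. The time point in Section 8.4.5 lies 90 days after the last scheduled test and 30 days after the end of stated follow-up. Both figures rest on counting the 120 days from the last dose, which Section 8.4.5 does not state. The 30 days should not be read as time since a contact that every participant receives.

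This is an internal inconsistency that should be corrected, because a site following the schedule to the letter would miss a stated safety requirement. It has no bearing on the preference endpoint at Cycle 6, the planned 144 participants, or the collection windows for adverse events. Which duration is right is a clinical decision that this review does not make.

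**What to change.** 1. Reconcile Section 8.4.5, the pregnancy-testing row of Table 1 and the follow-up wording in the Synopsis so that all three carry the same end point. The sponsor's clinical team decides which end point applies.
2. State in Section 8.4.5 what the period is counted from.
3. Check that the protocol-specified follow-up period in Table 6 agrees with the pregnancy reporting window in Section 8.5.1. Section 8.5.1 itself already points to the 120 days in Section 5.1.

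The cost is amendment wording. Whether any test or contact is added depends on the end point chosen. No statistical analysis changes.
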